#### 4.1.5 Brief physical examination

The brief physical examination will be conducted at the times specified in Table 1 and will include an assessment of the following:

- General appearance
- Cardiovascular
- Lungs
- Abdomen

Brief physical examination data to be recorded on the CRF will include: 1) normal/abnormal and 2) a description of any abnormalities

#### 4.1.6 Dietary assessment

During the screening period each prospective subject will participate in a 3-day diet diary assessment and analysis.

A trained investigative staff member will instruct subjects on how to complete a 3-day food diary. In addition, subjects will be taught how to estimate food quantities and how to record information regarding food brands and varieties in the diary. Subjects will be instructed not to change their personal eating habits during the 3-day diet assessment, but to eat normally and record all foods and quantities in the diary.

Each subject will record his or her food intake in a diary over 3 days during the screening period (2 days during the week and 1 day during the weekend). Subjects will return to the CRC with their record for analysis prior to Day -1.

A commercially available nutrition analysis software program will be used to analyze the dietary records. The results of the analysis will include the following:

- The contents of each meal and all snacks including all liquids consumed
- The total daily caloric intake for each day
- Total (in grams) carbohydrates, protein, fiber, and fat, (monounsaturated, polyunsaturated and saturated) for each day
- Percent of total caloric intake for each component (carbohydrates, protein, fiber, and fat)
- Dietary cholesterol (mg)
- Minerals (mg)
  - o Sodium
  - o Potassium
  - o Calcium
  - o Magnesium
  - o Phosphorus
  - o Iron
  - o Zinc
- Vitamins (mg)
  - o Total retinol
  - o Thiamine

- o Riboflavin
- o Niacin
- o Vitamin B6
- o Vitamin B12
- o Vitamin C
- o Vitamin D
- Vitamin E

Additionally, the analysis will provide an average of the same components for the 3 days.

These components, with the exception of the contents of each meal, will be recorded on the CRF.

## 4.2 Pharmacokinetic measurements

For timing of individual samples, refer to the study plan (Table 1) and/or Appendix C.

#### 4.2.1 Blood samples

Blood samples (4mL) for determination of rosuvastatin in plasma will be collected, processed, labeled and shipped as detailed in Appendices C and D. The date and time of collection will be recorded on the appropriate CRF.

#### 4.2.2 Collection and processing of biological samples

Plasma samples for measurement of rosuvastatin concentration will be analyzed by liquid chromatography/mass spectrometry/mass spectrometry (LC/MS/MS). Full details of the methodology will be included in the clinical trial report.

## 4.3 Pharmacodynamic measurements

Not applicable

## 4.4 Safety measurements

#### 4.4.1 Clinical laboratory assessments

Fasting blood samples (10 hours) for determination of clinical chemistry, hematology, and lipid profile parameters will be taken at the times given in the study plan (Table 1). The date and time of collection will be recorded on the appropriate CRF.

## 4.4.2 Urinalysis

A 10 mL midstream urine sample will be collected for urinalysis at the times given in the study plan (Table 1). If a sample is positive for protein or blood, a microscopic examination will be performed. Further investigations may be undertaken at the discretion of the investigator.

## 4.4.3 Serum pregnancy test

Female subjects of childbearing potential will have a serum pregnancy test conducted at the times specified in Table 1 for human chorionic gonadotrophin (HCG). The serum pregnancy test can be collected with the same sample as the blood chemistry. If the result is positive, the subject will not be allowed to proceed in the trial.

#### 4.4.4 HIV and hepatitis testing

Testing for HIV antibody, HBsAG, and hepatitis C antibody is to be performed on all subjects at screening. If a test result is positive, the subject will not be allowed to proceed in the trial. Although the results of the HIV and hepatitis screens have to be documented in the subject's file, they will not be collected on the CRFs and will therefore not be recorded in the study database.

#### 4.4.5 Sample collection

Samples will be collected in the following volumes specified:

Clinical chemistry/serum pregnancy	- 10mL
Hematology	- 10 mL
Lipid profile	- 10 mL
HIV/HBsAG/HepC	- 10 mL
Urinalysis	- 10 mL

The following laboratory variables will be measured:

Clinical chemistry	Hematology
Calcium	Hemoglobin
Phosphate	Hematocrit
Blood glucose	Platelet count
Total bilirubin	Red blood cell count
Alkaline phosphatase	White blood cell count with differential, including neutrophils, lymphocytes, monocytes, eosinophils, and basophils
Urea nitrogen (BUN)	
Uric acid	Lipid Profile
Chloride	Total cholesterol

Clinical chemistry	Hematology	
Carbon dioxide	TG	
Creatinine	LDL-C	
Total protein	HDL-C	
Albumin		
Aspartate aminotransferase (AST)	Urinalysis	Microscopic analysis of an formed element (if applicable)
Alanine aminotransferase (ALT)		
	pН	WBC
Sodium	Glucose	RBC
Potassium	Blood	Casts
Creatine kinase (CK)	Ketones	Crystals
Lactic dehydrogenase (LDH)	Protein	Epithlial cells
	Bilirubin	Bacteria
	Specific gravity	Mucous

#### 4.4.6 Electrocardiographic measurements

A standard resting 12-lead ECG will be obtained at screening only and will be recorded after the subject has been lying down for 10 minutes.

#### 4.4.7 Vital signs

For timing of individual measurements refer to study plan (Table 1).

Vital signs consist of a sitting heart rate, sitting blood pressure, and oral temperature.

Oral temperature will be measured in degrees Celsius (°C) at screening and Day –1 only.

AstraZeneca will provide the investigator reference range values for each vital sign measurement required by the protocol

#### 4.4.7.1 Blood pressure and heart rate

Heart rate and blood pressure will be measured after the subject has been seated for at least 5 minutes. Heart rate will be determined by palpation of the radial pulse for a period of 30 seconds and then multiplied by two. Blood pressure will be measured using a blood pressure device with an appropriate cuff size. The same arm will be used for each measurement.

## 4.5 Genetic sampling and storage

Blood samples will be obtained from each subject and used to prepare deoxyribonucleic acid (DNA) samples. Consent for genetic research will be obtained on a separate consent form and

is completely optional – ie, refusal to provide such consent does not preclude participation in the main pharmacokinetic study. The blood samples obtained under this consent will be exclusively used to study the effects of genetic polymorphisms on the disposition of rosuvastatin. Currently, genes of special interest include OATP-C (which encodes a hepatic uptake transport protein) and MRP2 (which encodes a transport protein implicated in the biliary excretion of statins). However, other genes implicated in the ADME of statins may also be studied. DNA samples will not be used in other types of genetic or non-genetic research either as test or control specimens.

Blood samples may be stored for up to a year prior to DNA extraction, and the extracted DNA may be stored for up to 15 years. DNA samples, and any remaining blood samples will be destroyed 15 years after study completion (defined here as database lock).

#### 4.5.1 Collection, labeling and shipment of genetic samples

Approximately 9 mL of blood will be collected for the genetic sample. Genetic samples will be collected, labeled and shipped as detailed in Appendix E.

# 4.6 Volume of blood sampling

The total volume of blood that will be drawn from each subject in this study is as follows:

Assessment		Sample volume (mL)	n of samples	Total volume (mL)
Blood sampling for rosuvastatin		4 mL	19	76 mL
Genetic sample		9 mL	1	9 mL
Safety	Clinical chemistry	10 mL	3	30 mL
	Hematology	10 mL	3	30 mL
	Lipid profile	10 mL	1	10 mL
	HIV/HBsAG/Hep atitis C	10 mL	1	10 mL
Total				165 mL

Table 5Volume of blood to be drawn from each subject

# 4.7 Adverse events

The definitions of adverse events (AEs), serious adverse events (SAEs) and other significant adverse events (OAEs) are given in Appendix B. Additional guidance on defining a SAE and determining causality are also included in Appendix B. It is of the utmost importance that all staff involved in the study is familiar with the content of these sections. The principal investigator is responsible for ensuring this.

#### 4.7.1 Recording of adverse events

Adverse events will be collected beginning Day –1 through final assessment on Day 4. SAEs will be collected from the time the informed consent is signed through final assessment on Day 4.

The following variables will be recorded for each AE:

Start date, stop date, maximum intensity, action taken, outcome, causality (yes or no) and whether it constitutes an SAE or not.

The intensity rating is defined as:

1 =mild (awareness of sign or symptom, but easily tolerated)

2 = moderate (discomfort sufficient to cause interference with normal activities)

3 = severe (incapacitating, with inability to perform normal activities)

It is important to distinguish between serious and severe AEs. Severity is a measure of intensity whereas seriousness is defined by the criteria in Appendix B. An AE of severe intensity need not necessarily be considered serious. For example, nausea that persists for several hours may be considered severe nausea, but not a SAE. On the other hand, a stroke that results in only a limited degree of disability may be considered a mild stroke but would be a SAE.

Should a pregnancy occur, it must be reported in accordance with the procedures described in Section 8.4, Procedures in case of pregnancy. Pregnancy in itself is not regarded as an AE unless there is a suspicion that an investigational product may have interfered with the effectiveness of a contraceptive medication.

#### 4.7.2 **Reporting of serious adverse events**

When the investigator becomes aware of an SAE during the course of the study, the SAE must be reported to the local monitor or other AstraZeneca representative within one (1) day.

All SAEs have to be reported, whether or not considered causally related to the investigational product. All SAEs will be recorded in the case report form. The investigator is responsible for informing the Ethics Committee and/or the Regulatory Authority of the SAE as per local requirements.

The AstraZeneca representative will work with the investigator to compile all the necessary information to ensure that the appropriate AstraZeneca Drug Safety Department receives a report by day one for all fatal and life-threatening cases and by day five for all other SAEs.

If a non-serious AE becomes serious, this and other relevant follow-up information must also be provided to AstraZeneca within 1 day as described above.

# 5. STUDY MANAGEMENT

# 5.1 Monitoring

The monitoring of this study will be performed in accordance with the principles of Good Clinical Practice (GCP) as laid out in the International Conference on Harmonization (ICH) document "Good Clinical Practice: Consolidated Guideline".

#### 5.1.1 Data verification

It is a prerequisite of this study that the study monitor has direct access to source data for data verification. This will be done by comparing data from the CRFs with those in the subject's medical notes (permission from the subject will be sought as part of the consent process). Such verification is an essential element of quality control, as it allows the rectification of transcription errors and omissions.

Monitoring will routinely be performed prior to the transfer of data to Data Management.

#### 5.1.2 Direct access to source data

Not applicable

# 5.2 Archiving of study documentation

AstraZeneca will retain all documentation pertaining to this study in the AstraZeneca central file for as long as rosuvastatin is available for human consumption.

The investigator will retain all documentation pertaining to this study for at least 15 years.

# 5.3 Audits and inspections

Authorized representatives of AstraZeneca, a regulatory authority, an Independent Ethics Committee (IEC) or an Institutional Review Board (IRB) may visit the center to perform audits or inspections, including source data verification. The purpose of an AstraZeneca audit or inspection is to systematically and independently examine all study related activities and documents to determine whether these activities were conducted, and data were recorded, analyzed, and accurately reported according to the protocol, GCP guidelines of the ICH and any applicable regulatory requirements. The investigator should contact AstraZeneca immediately if contacted by a regulatory agency about an inspection at his or her center.

# 5.4 Training of staff

The principal investigator will maintain a record of all individuals involved in the study (medical, nursing and other staff). He or she will ensure that appropriate training relevant to the study is given to all of these staff, and that any new information of relevance to the performance of this study is forwarded to the staff involved.

# 5.5 Changes to the protocol

Study procedures will not be changed without the mutual agreement of the principal investigator and AstraZeneca.

If it is necessary for the study protocol to be amended, the amendment and/or a new version of the study protocol must be notified to or approved by each IEC or IRB, and in many countries also the local regulatory authority, before implementation. Local requirements must be followed.

If a protocol amendment requires a change to a particular center's Master Written Informed Consent Form, then AstraZeneca and the center's IEC or IRB must be notified. Approval of the revised Master Written Informed Consent Form by AstraZeneca and by the IEC or IRB is required before the revised form is used.

AstraZeneca will distribute amendments and new versions of the protocol to each principal investigator who in turn is responsible for the distribution of these documents to his or her IEC or IRB, and to the staff at his or her center. The distribution of these documents to the regulatory authority will be handled according to local practice.

# 5.6 Study agreements

The principal investigator at each center must comply with all the terms, conditions, and obligations of the study agreement for this study. In the event of any inconsistency between this protocol and the study agreement, this protocol shall prevail.

# 5.7 Study timetable and termination

The study is expected to start on and to be completed by

# 5.8 Data management

## 5.8.1 Case report forms

CRFs will be used to record all data not captured electronically. The forms will be in triplicate on carbonless paper. Data should be recorded directly and legibly from the source documents onto the CRFs in black ballpoint pen. Corrections to the CRFs should be made legibly, initialed, and dated. Correction fluid or covering labels must not be used. The top and middle sheets will be collected and forwarded to data management personnel. The bottom sheet will be retained in the Investigator Study File.

The AstraZeneca Monitor will check data at the monitoring visits to the investigational site. The Investigator, together with the AstraZeneca Monitor, will ensure that the data in the CRFs are accurate, complete and legible.

AstraZeneca Data Management will enter the CRF data on an ongoing basis into their standard commercial database. The data will be verified and cleaned with electronic data checks comprised of validated computer programs and manual data review. Any missing,

impossible or inconsistent recordings in the CRFs will be referred back to the Investigator using a data clarification form (DCF), and be documented for each individual subject before Clean File Data status is declared. Responses should be received by Data Management and updated within an agreed number of days upon generating the data queries. These timelines will be reduced nearing Clean File. Clean File will be declared when all of the following have been completed: all data discrepancies are resolved or accepted; all SAEs have been reconciled with the clinical database; all coding is complete and has been medically reviewed and approved; and quality control of the database against the CRF and relevant data sources has been completed.

## 5.8.2 Genetic data

Genetic data will not be collected on the CRFs. The results of genetic research will be confidential. The results of any genetic research, any genetic sequences, cell lines, patents, diagnostic tests, drugs and biological products developed directly or indirectly from those samples, are the sole property of the study sponsor (and its successors, licensees, and assignees). Genetic data may be reviewed with research collaborators and published. Otherwise, no genetic data will be provided to the subject, the subject's family, the investigator, or any other physician who is treating the subject or who may treat the subject in the future. Neither the subject's insurance company nor the subject's employer will have any access to these research results. There is no direct benefit to the subject in having genetic research performed.

# 6. STATISTICAL METHODS AND DETERMINATION OF SAMPLE SIZE

## 6.1 Statistical evaluation

A comprehensive SAP will be prepared and finalized before database lock.

# 6.2 Description of outcome variables in relation to hypotheses

Although there are no hypotheses to be addressed in this protocol, this section will list the outcome variables related to the objectives.

**Rosuvastatin exposure (primary objective):** After a single oral dose of rosuvastatin,  $C_{max}$  and AUC will be determined for each subject. If AUC data cannot be determined in all subjects completing the study, AUC(0-t) will replace AUC as a primary endpoint.

**Rosuvastatin exposure (secondary objective):** The following pharmacokinetic parameters will be estimated and summarized:  $AUC_{(0-t)}$ ,  $t_{1/2\lambda z}$ ,  $t_{max}$ , and CL/F. With exception to CL/F, these pharmacokinetic parameters, along with  $C_{max}$  and AUC, will also be estimated and summarized for N-desmethyl rosuvastatin and rosuvastatin lactone.

**Safety and tolerability (secondary objective):** Incidence and severity of adverse events, blood pressure/heart rate (sitting), laboratory parameters (hematology, clinical chemistry, urinalysis), and physical examination.

**Pharmacogenetic objective:** Genes of interest include OATP-C and MRP-2, and may include any other gene that may be involved with the ADME of statins. Genetic information will not be included in the SAP or study report.

# 6.3 Description of analysis sets

There are two populations in this study. All subjects receiving the dose of study drug will be included in the safety population. The per-protocol (PP) population, also known as the evaluable population, is defined as a subset of the safety population, excluding those subjects with a protocol deviation felt to significantly influence the pharmacokinetics of the drug. In order to be evaluable, subjects must have completed all study procedures from the screening period to the final blood sampling for plasma levels of rosuvastatin. Definitions of all such protocol deviations will be made in the SAP. Examples include, but are not limited to, major changes in the administration of study drug or co-administration of medications expected to affect the pharmacokinetics.

All safety data will be summarized using the safety population (defined as any subject who received the dose of study drug). Pharmacokinetic data will be summarized using the PP population. In the case of the PP and safety populations being identical, only the safety population will be used throughout; this decision will be made at the time of data review and documented in the SAP.

A test for homogeneity of variance in  $C_{max}$  and AUC will be performed for the subjects in the Asian groups. If the test shows no difference and the means appear similar, then the data will be pooled. This data will be related to pharmacokinetic data generated from the subjects in the Caucasian control group.

The distribution of  $C_{max}$ , AUC and AUC(0-t) values for the Caucasian control group and for the Asian subjects residing in the United States will be summarized using descriptive statistics and presented graphically (e.g. box and whisker plots). There will be no statistical comparisons between groups.

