## 6.4.2 Pharmacokinetics

 $C_{max}$  and  $t_{max}$  for each subject will be determined by inspection of the rosuvastatin plasma concentration-time profile. The terminal elimination rate constant ( $\lambda_z$ ) will be calculated by log-linear regression of the terminal portion of the concentration-time profiles where there are sufficient data (a minimum of 3 plasma concentration values in the terminal log-linear phase, spanning an interval of at least 2 half-lives.) Terminal elimination half-life ( $t_{\nu_2\lambda_z}$ ) will be calculated as  $0.693/\lambda_z$ . The AUC(0-t) will be calculated by the linear trapezoidal rule (AUC = AUC(0-t) + Clast/ $\lambda_z$ ). AUC(0-t) will be extrapolated to infinity using  $\lambda_z$  to obtain AUC where there are sufficient data. Following the single dose administration of rosuvastatin, the CL/F will be calculated as Dose/AUC.

Pharmacokinetic data,  $C_{max}$ , AUC(0-t) and AUC, will be summarized for each Asian ethnic group and pooled, if appropriate, using descriptive statistics, including geometric means and coefficient of variation, and listed. In addition, 95% CI for the mean pharmacokinetic parameters will also be presented.

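### Pooling of the six Asian groups hangs on a variance test plus an undefined look at the means, so whether a pooled summary is related to the Caucasian control depends on a poor criterion

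*Protocol*

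**What the plan says.** Section 6.3 plans "A test for homogeneity of variance in" Cmax and AUC among the Asian groups, and continues: "If the test shows no difference and the means appear similar, then the data will be pooled". The next sentence reads: "This data will be related to pharmacokinetic data generated from the subjects in the Caucasian control group". Read in sequence, it is the pooled data that are set against the control. Section 6.3 names no test, scale or significance level. It gives no figure for how close the means must be, and does not say what happens if Cmax and AUC point different ways.

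Section 6.4.2 says that Cmax and the two AUC measures "will be summarized for each Asian ethnic group and pooled, if appropriate, using descriptive statistics, including geometric means and coefficient of variation, and listed", and adds that "95% CI for the mean pharmacokinetic parameters will also be presented". So the group summaries do not depend on the pooling decision. The Statistical Methods part of the synopsis also summarises each ethnic group and does not mention pooling.

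Section 6.2 opens: "Although there are no hypotheses to be addressed in this protocol". Section 6.5 rules out formal comparison with the Caucasian group. The primary objective (section 2.1) is to summarise exposure in subjects of Asian heritage and relate it to the control. It does not name a pooled estimate.

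**The concern.** Pooling into one exposure figure makes sense if the groups have similar exposure levels. The only formal test in the rule concerns spread instead. Two groups can have the same coefficient of variation and different geometric means, or the reverse. A non-significant result would not show equality even if the test were about means.

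The condition that does concern means has no margin and is applied by eye to observed results. Two analysts could look at the same six geometric means and decide differently. At stake is whether a pooled Asian figure is set beside the control, and whether that figure mixes groups that differ. Pooling also makes the interval look much more precise than a single group's.

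Differences among the groups are plausible. Section 1.3 calls the difference from Caucasians similar only for Chinese and Japanese subjects. It gives no size for Indian subjects and no data for Filipino, Korean or Vietnamese subjects.

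**Working it through.** **The plan's own figures.** 6 × 22 = 132 evaluable and 6 × 26 = 156 recruited, as stated. The 22 per group has no variability or precision target behind it, so the behaviour of the rule has to be simulated.

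**Inputs.** From the protocol: six groups, 22 per group, and reporting by geometric mean and CV (section 6.4.2), which makes the log scale the natural one. Assumed, because the protocol does not give them: log-normal data, between-subject CV of 30% to 60%, and tests at the 5% level. Log-scale SD = √ln(1 + CV²). There were 4,000 trials per scenario, so the Monte Carlo standard error is at most √(0.25/4000) = 0.8 percentage points.

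**1. Log scale: does the variance test respond to mean differences?** Share of trials in which Bartlett's test passes, with true group geometric means spread evenly from smallest to largest:

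| True largest/smallest ratio | CV 40% | CV 50% | CV 60% |
|---|---|---|---|
| 1.0 | 94.7% | 95.2% | 95.1% |
| 1.25 | 94.4% | 95.2% | 94.6% |
| 1.5 | 95.0% | 94.3% | 95.1% |
| 2.0 | 95.2% | 95.0% | 94.8% |

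It does not. Mean-centred Levene on logs behaves the same way (93% to 95%). The test can also block pooling when geometric means are equal: with CV 40% in five groups and 60% in one, log-scale Levene rejects 36% of the time.

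**2. Raw scale: how often are six identical groups rejected?**

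| Test | CV 40% | CV 50% | CV 60% |
|---|---|---|---|
| Bartlett | 34% | 47% | 61% |
| Levene, mean-centred | 13% | 17% | 22% |
| Levene, median-centred | 3.7% | 4.0% | 4.5% |

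Because SD rises with the mean, a raw-scale test does react indirectly to mean differences. At CV 40%, mean-centred Levene passes 87%, 79%, 64% and 30% of the time at true ratios of 1.0, 1.25, 1.5 and 2.0. The rule's behaviour therefore depends on a test and a scale that it does not name.

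**3. Can the eye do the rest?** Observed ratio of the largest to the smallest group geometric mean at CV 40%:

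| Truth | Median | 5th to 95th percentile |
|---|---|---|
| Six identical groups | 1.22 | 1.11 to 1.39 |
| Even spread, true ratio 1.25 | 1.35 | 1.17 to 1.56 |
| One group at 2-fold | 2.20 | 1.88 to 2.58 |

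A 2-fold group stands clear of chance variation. A 1.25-fold range does not, because its observed ratios overlap heavily with those of identical groups.

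**4. What pooling does to the figure.** The 95% CI factor for a geometric mean is exp(t × SD/√n). At CV 40%, SD = √ln(1.16) = 0.385.
- One group, n = 22: exp(2.080 × 0.385/√22) = 1.19.
- Pooled, n = 132: exp(1.978 × 0.385/√132) = 1.07.

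With six means spread evenly on the log scale over a 1.25-fold range, the pooled value sits at the midpoint, and the highest group lies a factor √1.25 = 1.12 above it. That is outside a typical pooled interval of ×/÷ 1.07. The interval is a fair statement about the average but not about each group.

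**5. Would a test of means rescue the rule?** Only partly. One-way ANOVA on logs with p > 0.05 as the criterion would still pass a true 1.25 ratio 64% of the time at CV 40%, and 83% at CV 60%.

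**The case against.** The rule has two conditions, and the second is about means. A reader might infer that a group with 2-fold exposure would be pooled 95% of the time. That figure describes the log-scale variance test alone. With one group at 2-fold, the observed ratio exceeds about 1.8 in 95% of trials at CV 40% to 60%, and such means would hardly be called similar. This objection stands. The weakness lies in modest differences.

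A reader might also infer that the study's headline result is data-driven, or that a high-exposure group could be hidden. The protocol does not support either. Section 6.4.2 summarises every Asian group whatever the pooling decision, no pooled estimate is primary, and no hypothesis is tested, so no type I error rate is at stake.

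Nor does every raw-scale variance test reject too often: median-centred Levene does not. The statement in section 6.3 that groups will not be compared statistically closes a paragraph about the Caucasian and Asian distributions. Sections 6.4.1 and 6.5 limit the same idea to comparison with Caucasians, so a variance check among Asian groups need not contradict it. The open-label design adds little, since groups are defined by heritage and concentrations come from a laboratory assay.

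Last, the test, scale, level and margin could be set in the analysis plan, which section 6.1 requires before database lock. That is true of those details. But the protocol itself has chosen a variance test as the formal criterion for pooling exposure levels, and an analysis plan that only filled in details would keep that choice.

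**Conclusion.** The point holds in a limited form. Section 6.3 fixes a poor criterion for deciding, after the data are seen, whether a pooled Asian summary is formed and related to the Caucasian control. On the log scale the variance test tells nothing about exposure levels. On the raw scale two common versions would often block pooling of identical groups (34% to 61% for Bartlett, 13% to 22% for mean-centred Levene, at CV 40% to 60%). The check by eye would probably catch a gross outlier but cannot separate a 1.25-fold range from chance at 22 per group.

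The CV range, log-normal shape and 5% level are assumptions. The finding that the log-scale test does not respond to means does not depend on the CV chosen; the other percentages do. Because group results are reported either way and the study is descriptive, this should be fixed but is not critical to its validity.

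**What to change.** In sections 6.3 and 6.4.2:

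- Delete the variance test and the judgement on similarity of means as conditions for pooling.
- State that the main presentation relates each Asian group's geometric mean and 95% CI to those of the Caucasian control.
- Always give one pre-specified, supplementary overall Asian estimate: the equal-weight average of the six group log means, back-transformed, with its 95% CI. The standard error on the log scale is (1/6) × √(Σ sᵢ²/nᵢ), where sᵢ and nᵢ are each group's log-scale SD and size. No model beyond the group summaries is needed.
- Print the smallest and largest group geometric means beside it.

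The cost is wording, with no added subjects, samples or assays. One small downside is that an overall figure will appear even when the groups differ, which is why the between-group spread must stand next to it.
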